CASTomize Pilot Study Protocol

Principle investigator: [name]

Co-investigator: [name], [name]

Industrial collaborator: [name], [name], [name]

CASTomize pilot study protocol: a randomized controlled trial comparing CASTomize 4D printed cast versus standard of care fiberglass cast on fracture reduction and patient reported outcomes.

Abstract

Background: For many years, traditional fibreglass casting has been the gold standard of immobilisation for distal radius fractures (DRFs). However, the traditional method of casting has obvious disadvantages such as poor patient comfort, inability to be in contact with water, difficulty observing skin underneath and requiring multiple cast changes in the patients care journey. This study compares the Castomize 4D printed casts versus the conventional fiberglass cast in fracture immobilisation, and various patient reported outcomes.

Methods/design: This study is a randomised control trial comparing Castomize 4D printed cast versus conventional fibreglass casts in isolated conservatively treated distal radius fractures. The primary outcome measure is fracture reduction. Secondary outcome measures include patient reported outcome measures such as the Adult Rated Cast Evaluation Questionnaire (ARCEQ)[1][2], comfort of the cast, quality of life assessed with the EQ-5D-5L questionnaire[3], cost-effectiveness and adverse events occurrence. In total, 30 patients will be included and followed for 6 months.

Trial registration: Pending

Registration number: Pending

Background

Displaced distal radius fractures (DRF) are very common in the adult population and their incidence is still on rising trend due to aging population. This is an issue which is pervasive across all ages, but most common in the elderly. In 2019, 180 million fractures happened worldwide. An average of 5 fracture incidents occurs every second. The current gold standard in fracture immobilisation is via the application of a fibreglass cast. However, the current fibreglass cast has multiple disadvantages. The cast is bulky, has poor ventilation and cannot come into contact with water. This gives patients considerable discomfort, and are unable to bathe and provide hygiene to their injured limb for the duration of the casting. Because the cast is not breathable, skin maceration, itchiness and wounds

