Patients randomized to group 1 will undergo fracture immobilisation with the Castomize 4D printed cast via the care team (Casting technician/ clinical team). The Castomize 4D printed cast is appropriately heated and then moulded to the patients wrist as per usual manipulation and reduction techniques. The cast is held in position until hardened.

Group 2: Conventional casting (Figure 1)

Patients randomized to group 2 undergo fibreglass casting as per the standard of care.

In both groups, post casting X-rays are taken to assure fracture reduction and recasting may be attempted in the event of inadequate fracture reduction.

A patient information sheet will be provided to the patient explaining the study protocol, and what to look out for in caring for their casts.

Inclusion criteria

- Age \geq 21 years
- Distal radius fracture for conservative treatment within 3 weeks of initial injury

Exclusion criteria

- Concomitant injuries to the ipsilateral extremity, interfering with the treatment of the DRF (Example: concomitant elbow fracture that requires further immobilisation with a above elbow cast)
- Inability to complete study forms due to any cognitive, mental issues.
- Pregnant women

Study procedures and timeline

Measurements will take place at 6 time points as shown in Table 1. These time points are baseline (T0), 1 week (T1), 2 weeks (T2), 6 weeks (T3), 3 months (T4) and 6 months (T5) after inclusion in the study. At T0, baseline characteristics will be gathered. An inclusion form will be filled in by the treating physician providing fracture and treatment-specific information. Second, patients receive a questionnaire, providing predominantly patient and injury-specific information. The list of baseline characteristics is shown in Table 2. Patients receive questionnaires at T1 to T5. These questionnaires are carried out by phone call. Posterior-anterior (PA) and lateral radiographs of the wrist will be taken at T0 (before and after reduction) and during follow-up at T1 –T4 as per standard of care. Physical examination of the wrist will take place at T4 and will be performed by the research team. Study visit may be administered via phone call. Functional tests will be performed at patient earliest appointment.

Table 1 Schedule of activities

	T0 Baseline	T1 D7 \pm 3	T2 D14 \pm 3	T3 D35 \pm 7	T4 D84 \pm 14	T5 D168 \pm 21
Inclusion form	✓					
X-rays*	✓	✓	✓	✓	✓	
Functional tests**					✓	✓
VAS		✓	✓	✓	✓	✓
Photograph		✓				
Comfort of cast		✓	✓	✓		

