Analgesic use		✓	✓	✓	✓	✓
EQ 5D5L		✓***		✓	✓	✓
ARCEQ				✓	✓	✓
MCQ- iMTA				✓	✓	✓

PCQ- iMTA				✓	✓	✓
-----------	--	--	--	---	---	---

*X-rays before and after reduction (obtained from standard of care results if available)

**ROM, grip strength done by study team. ROM, DRUJ and Kapandji will be collected as part of standard of care if available

*** EQ 5D5L status pre-fracture and post-fracture sustainment

Table 2 Baseline characteristics

Baseline characteristics	
Date of emergency room visit	Sex
Affected wrist	Date of Birth
Method of reduction	
	Hand dominance
	Mechanisms of injury
	Smoking Status
	General medical history
	Previous injuries of the affected extremity
	La Fontaine criteria

Outcome

Primary outcome The primary outcome of this study is the occurrence of fracture displacement assessed on PA and lateral radiographs at 1, 2 and 6 weeks. Displacement of the radius is defined by: As compared to the post reduction radiograph at T0, Displacement of : > 15° of dorsal angulation, > 20° of volar angulation, < 15° of radial inclination, > 3mm of radial shortening and > 2mm intraarticular step-off or gap. Measurements will be on standard PA and lateral radiographs of the wrist by trained members of the research team.

Secondary outcomes An overview of measurements is shown in Table 1.

- Comfort of the cast assessed via pictorial representation of pressure marks or areas of discomfort.
- Severity of pain evaluated with the Visual analogue Score (VAS)
- Patient will describe their average wrist symptoms over the past week on a scale of 0-10 using Adult Rated Cast Evaluation Questionnaire (ARCEQ) [6][7].
- Quality of life will be assessed using the 5-level EuroQol (EQ-5D-5L) scoring questionnaire.
- Cost-effectiveness will be measured using the Medical Consumption Questionnaire (iMCQ) and the Production Consumption Questionnaire (iPCQ) [8].
- Physical examination:
 - Range of motion (ROM) of the wrist will be measured with a goniometer. ROM concerns dorsal flexion, volar flexion, radial deviation, ulnar deviation, pronation and supination.
 - Grip strength will be measured with a Jamar hydraulic hand dynamometer. The maximum score for each side over 3 attempts will be used
 - Specific testing of the wrist and hand will be performed namely:
 - distal radioulnar joint (DRUJ) stability tested with the DRUJ ballottement test

- opposition of the thumb using the Kapandji score

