- finger stiffness will be measured with finger-to-palm distance, tested from the tip of the finger to the distal palmar crease when the fingers are in maximal active flexion

ROM and grip strength on the injured side will be compared with the uninjured side.

- Number of conversions to surgical treatment and other (serious) adverse events will be monitored. (Eg: Skin complications)

It is expected that a proportion of patients will fail conservative treatment with displacement of the distal radius fracture at week 1 or week 2 follow up. These patients will continue with surgical fixation of their fractures and no further trial procedures will be required.

Adverse events reporting

All adverse events reported by the patient or observed by the treating physician or researcher will be recorded. Serious adverse events (SAE) will be reported to the Domain Specific Review Board (DSRB), which approved the protocol.

Serious adverse events are defined as:

- Skin related problems requiring surgical intervention (Eg: Ulcer, infection, necrosis)
- Compartment syndrome
 - Cast related injury to the patient resulting in loss of limb or life

Study related serious adverse events are defined as:

- Compartment syndrome

Fig 1 Conventional Fiberglass cast[9]

Fig 2 CASTomize 4D printed cast

Data analysis

General descriptive statistics will be performed on baseline patient and fracture characteristics. Patients will be analysed according to the intention-to-treat principle.

Primary outcome

The primary outcome, fracture re-displacement, will be analysed using a mixed-effects logistic regression. To account for clustering, a random intercept for the hospitals will be used. Fixed effects will be the covariates we adjust for as reported in the literature, namely age, presence of osteoporosis, and fracture characteristics. If new prognostic factors will be identified and reported in the literature, these factors will also be added as covariates.

Secondary outcomes

For secondary outcomes, trends between baseline and follow-up time points (T0-T5) will be assessed using linear mixed models for repeated measures. This accounts for comfort of the cast, recovery of function and grip strength, pain severity (VAS), ARCEQ and EQ-5D-5L scores. The number of conversions to surgical fixation and complications will be determined using Fisher Exact or Chi-square test, depending on the magnitude of results.

Cost-effectiveness analysis

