Both cost-effectiveness (CEA) and cost-utility (CUA) analysis will be performed from a societal perspective. For the calculation of medical costs, we will use charges as published in Singapore guidelines as a proxy of real costs. The unit per price of the cast application in patients with DRF will be calculated with the microcosting method. Intramural costs (i.a. additional diagnostics, number of hospital visits, in case of hospital admission the length of stay etc.) are collected from the electronic health record. Productivity costs will be registered in detail by the iPCQ. The iMCQ and the iPCQ are validated by the Institute of Medical Technology Assessment (Erasmus University, Rotterdam, The Netherlands).

The difference in costs and effects of CASTomize instead of a circumferential cast will be calculated as incremental cost-effectiveness ratio (ICER). The primary effect outcome measures will be the number of re-displacements for the CEA and quality-adjusted life years (QALY) for the CUA. QALYs will be measured, based on the Singaporean tariff for the EQ-5D-5L.

The sensitivity analysis will assess the robustness of the results to changes in costs and effect parameters. Bootstrapping with 1000 replications will be used to estimate 95% confidence intervals around cost differences and the uncertainty surrounding the ICERs. This will be graphically presented on cost-effectiveness planes and acceptability curves using the net benefit framework. For the time horizon of 6 months, discounting is not necessary.

Data management

All data are handled confidentially and anonymized in compliance with the Singapore Personal Data Protection Act (PDPA). Personal data of participants will be changed by a study number. This number is used for all study documentation, study reports and publications. The key of this study number will be handled by an independent researcher. During the study period, all data will be collected and managed using GemsTracker electronic data capture tools. Paper case report forms are entered in GemsTracker by the researcher and the original paper case forms will be filed in the investigator site file at the recruiting hospital. All data is stored for 10 years.

Data monitoring

Since the study is labelled as low risk, a data safety monitoring board is not required.

References

- [1] M. Neubauer, "DASH Score," *Heartbeat Medical*, Jul. 22, 2021. <https://heartbeat-med.com/resources/dash-score/> (accessed Nov. 06, 2022).

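### Patients who displace at week 1 or 2 and have surgery leave trial data collection, so the 6-month secondary, QALY and productivity-cost comparisons cannot be made on all randomised patients

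*Combined protocol and SAP*

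**What the plan says.** The last paragraph of the secondary outcomes (Outcome section) anticipates that some fractures will displace by the week 1 or week 2 visit, without giving a rate. Of those patients it says: "These patients will continue with surgical fixation of their fractures and no further trial procedures will be required".

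Other parts of the plan make no exception for them:

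- Abstract, Methods/design: "In total, 30 patients will be included and followed for 6 months".
- Data analysis: "Patients will be analysed according to the intention-to-treat principle".
- Data analysis, Secondary outcomes: "trends between baseline and follow-up time points (T0-T5) will be assessed using linear mixed models for repeated measures".
- Study procedures and timeline: questionnaires run from T1 to T5, and "These questionnaires are carried out by phone call".
- Cost-effectiveness analysis: QALYs come from the EQ-5D-5L over a 6-month horizon, and "Productivity costs will be registered in detail by the iPCQ".

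Table 1 schedules EQ-5D-5L at T1, T3, T4 and T5; ARCEQ, iMCQ and iPCQ at T3, T4 and T5; and functional tests at T4 and T5. A footnote adds that "ROM, DRUJ and Kapandji will be collected as part of standard of care if available".

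The plan does not say how displacement or surgery enters the mixed models, or how missing values after surgery are handled.

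**The concern.** This is not ordinary dropout. Follow-up stops because the patient has had the primary outcome event by week 2, and whether that event is as frequent with one cast as with the other is the trial's main question. If early failures differ between arms and later fare differently from other patients, dropping them distorts every comparison from T3 onward. Results at T3-T5 would then describe mainly the patients whose fractures held, or be extrapolated from them.

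The economic analysis is mismatched in the same way. The cost-effectiveness analysis counts re-displacements in all randomised patients. For those who exit early, the cost-utility analysis has almost no measured utility and the iPCQ supplies no productivity data.

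**Working it through.** **The plan's own figure.** The plan states 30 patients followed for 6 months, with no derivation to reproduce. Taken at face value, the T3-T5 analysis set is 30 of 30. The check is what remains of that under the exit rule.

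**What one early exit costs.** Counts are from Table 1, assuming everything due up to and including the exit visit is collected.

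| Item | Planned | Obtained, exit at T1 | Obtained, exit at T2 |
|---|---|---|---|
| VAS | 5 | 1 | 2 |
| Analgesic use | 5 | 1 | 2 |
| Comfort of cast | 3 | 1 | 2 |
| EQ-5D-5L | 4 | 1 | 1 |
| ARCEQ | 3 | 0 | 0 |
| iMCQ | 3 | 0 | 0 |
| iPCQ | 3 | 0 | 0 |
| Study-team functional tests | 2 | 0 | 0 |
| Total | 28 | 4 | 7 |

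EQ-5D-5L is not scheduled at T2, so even a week-2 failure has only the day-7 value: 168 - 7 = 161 days, and 161/168 = 96% of the horizon is unmeasured.

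**How many patients.** The plan gives no failure rate. Assuming 10% to 30%: 30 x 0.10 = 3 and 30 x 0.30 = 9 patients without T3-T5 questionnaires. At a 10% rate, the chance of at least one such patient among 30 is 96%.

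**Size of the bias.** If converted patients differ from the others by the same gap in both arms, and the others do not differ between arms, then

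hidden difference = (difference in failure rate) x (outcome gap).

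Assume 15 per arm (the plan states no allocation ratio) and failure of 40% v 20%, that is 6 v 3, leaving 9 v 12 patients.

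- Utility gap -0.10: 0.20 x -0.10 = -0.02. Gap -0.20: -0.04. Gap 0: nothing hidden. Gap +0.10: +0.02.
- As QALYs, with the gap constant over the unmeasured time: 0.02 x 161/365.25 = 0.009 and 0.04 x 161/365.25 = 0.018.
- Productivity, with an assumed 20 extra days off work per converted patient: 0.20 x 20 = 4.0 days per randomised patient, where those who remain would show 0.
- A milder case, 2 v 1 failures of 15: (1/15) x 0.10 = 0.007 and (1/15) x 0.20 = 0.013. With equal failure rates the hidden difference is 0.

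**Against sampling error.** Assume a utility SD of 0.15 to 0.20.

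- At 15 v 15: SE = SD x sqrt(2/15) = 0.055 to 0.073.
- At 9 v 12: SE = SD x sqrt(1/9 + 1/12) = 0.066 to 0.088.
- Bias relative to the full-data SE: 0.02/0.073 = 0.27 up to 0.04/0.055 = 0.73. In the milder case: 0.007/0.073 = 0.1 up to 0.013/0.055 = 0.24.

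**Does the mixed model recover it?** Take T1 and T5 utility with correlation 0.5 and equal SDs, T5 missing in failures, and failure of 40% v 20%. The likelihood estimate is the completers' difference plus slope x the shift in T1 means due to the failures.

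- Failures have the same T1 utility as others: shift 0, estimate 0.00, when the truth is -0.02 or -0.04.
- Failures 0.05 lower at T1: shift = (0.40 - 0.20) x -0.05 = -0.01; times 0.5 = -0.005, against the same truths.

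A simulation with 2,000,000 patients per arm (SD 0.18) gave the same results. The model corrects only to the extent that the T1 value foretells the later gap. For ARCEQ, iPCQ and study-team function, these patients have no follow-up value from which to borrow.

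**The case against.** The exit sentence says procedures are not required; it does not forbid collection or withdraw the patient, and the T1-T5 questionnaire schedule carries no exception. On that reading this is an ambiguity. But nothing commits anyone to collecting the data, and optional collection could differ by arm, so the passages still need reconciling.

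Intention-to-treat is strictly a rule about grouping patients, and missing data do not breach it. That is fair: the plainest contradiction is with the 6-month follow-up. In practice, though, the analysis cannot include all randomised patients at T3-T5 if some have no data there.

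The exit covers only displacement at week 1 or 2. Patients who displace at week 6 are not covered by it, so not every failure is lost. Part of the 161-day gap also reflects Table 1 having no T2 EQ-5D-5L for anyone; after a T2 exit, 154 days remain. Both points narrow the effect without removing it.

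The bias is below one standard error even in the larger example, and this is a pilot. That stands. It is nonetheless systematic and avoidable. The sensitivity analysis planned for the economic evaluation can vary assumptions but cannot recover data that were never collected.

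ARCEQ might be thought irrelevant once the cast is off, but the plan describes it thus: "Patient will describe their average wrist symptoms over the past week on a scale of 0-10". Table 1 runs it to T5. If it were dropped after surgery, the case for EQ-5D-5L, iMCQ, iPCQ and VAS would be unchanged.

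**Conclusion.** The concern holds. As written, the exit rule contradicts the stated 6-month follow-up and leaves the intention-to-treat analysis of the secondary, QALY and productivity-cost outcomes without data on early failures. That these data go uncollected follows from the documents alone.

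The size of any bias does not. Failure rates, utility gaps, SDs, the correlation and 15 per arm are all assumptions. Under them, the hidden utility difference runs from zero (no gap, or equal failure rates) to 0.04 in either direction if the gap can be as large as 0.20 either way; losing 9 of 30 patients as 6 v 3 also raises the SE from 0.055-0.073 to 0.066-0.088. The primary outcome, the number of conversions and health-record costs are not affected. This should be fixed, but it does not threaten the primary comparison.

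**What to change.** Replace the clause releasing these patients from trial procedures with:

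> Patients who convert to surgery remain in trial follow-up to T5. VAS, analgesic use, EQ-5D-5L, ARCEQ, iMCQ and iPCQ continue by phone as scheduled in Table 1, and functional tests are done at T4 and T5 where attended. Only comfort of cast stops when the cast is removed.

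In the Data analysis section, state that the secondary and cost analyses include all randomised patients in their randomised arm, with outcomes after surgery counted. Report by arm how many converted patients gave data at each visit.

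If the sponsor prefers a different target for converted patients, it should define that target and its missing-data handling in advance. That alone would not supply the 6-month utilities and productivity costs the economic analysis needs.

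The cost is a protocol amendment and at most four further contacts (T2-T5) for each converted patient: for 3 to 9 patients, 3 x 4 = 12 to 9 x 4 = 36 at most, with instruments already in use. Functional tests add some in-person work, since grip strength cannot be measured by phone. The primary outcome definition, the surgical decision and clinical care are unchanged. The amendment should come before converted patients leave follow-up, because the data cannot be recovered later by analysis.

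### The study-related SAE definition names compartment syndrome only, so two of the three listed SAE types are classed as not study-related even when the cast caused them

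*Combined protocol and SAP*

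**What the plan says.** The Adverse events reporting section gives two definitions, one after the other.

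- **Serious adverse events**, three entries: "Skin related problems requiring surgical intervention (Eg: Ulcer, infection, necrosis"), "Compartment syndrome", and "Cast related injury to the patient resulting in loss of limb or life".
- **Study-related serious adverse events**, introduced by "Study related serious adverse events are defined as", one entry: compartment syndrome again.

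The same section sets the recording rule, "All adverse events reported by the patient or observed by the treating physician or researcher will be recorded", and the reporting rule, "Serious adverse events (SAE) will be reported to the Domain Specific Review Board (DSRB), which approved the protocol". The Data monitoring section adds: "Since the study is labelled as low risk, a data safety monitoring board is not required".

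**The concern.** The two definitions do not fit together. Both randomised groups are treated with a cast, so the cast is the study intervention whichever arm a patient is in. An injury that the protocol itself describes as caused by the cast should therefore be study-related, yet the second definition leaves it out. It also leaves out skin events that need surgery. Yet the Background gives skin and soft-tissue problems under a cast as a reason for developing the new device, and the secondary outcomes name skin complications as the example of an adverse event.

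At stake is any statement in the trial report about study-related SAEs. A reader of a pilot study of a new device will look for that figure. Under the present wording it could be zero even if a cast had caused an ulcer that needed surgery. With no data safety monitoring board, the classification rests on the protocol text and the study team.

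**Working it through.** There is no figure to reproduce. The check sets the two lists side by side and then traces where the study-related label is used.

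**Step 1. Compare the lists** (Adverse events reporting).

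| Event type | SAE list | Study-related SAE list |
|---|---|---|
| Skin problem needing surgery | yes | no |
| Compartment syndrome | yes | yes |
| Cast-related injury with loss of limb or life | yes | no |

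Three types are serious and one is study-related, so 3 − 1 = 2 types are left out.

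**Step 2. Is the second list closed?** It is worded as a definition and carries no marker that its entry is an example. The protocol does mark examples elsewhere, for instance in the skin entry of the SAE list. The single entry is complete as printed and is followed by the figure captions, so nothing suggests that entries were lost. No other section widens the definition or describes a case-by-case causality assessment.

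**Step 3. Apply the rule to cases.**

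- *Cast-related death or limb loss without compartment syndrome:* serious, not study-related. This is a direct contradiction, because attribution to the cast is part of the SAE entry itself.
- *Skin necrosis under the cast, treated surgically, without compartment syndrome:* serious, not study-related. The skin entry does not itself state a cause, so the fault here is that the rule excludes the event even when the cast did cause it.
- *Limb loss following compartment syndrome:* study-related, through the compartment syndrome entry. The exclusion is therefore not absolute for the third category.
- *Compartment syndrome with a cause other than the cast:* study-related by definition. The rule errs in this direction too.

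**Step 4. Trace the label through the plan.**

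- Recording covers all adverse events, related or not.
- Reporting to the review board covers all SAEs, with no condition on relatedness.
- The secondary outcome in the Outcome section counts conversions to surgery and other adverse events, serious or not, without a relatedness filter.
- The Data analysis section compares conversions and complications by Fisher's exact or chi-square test, again without such a filter.
- No action, timeline or analysis is attached to the study-related category.

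The mismatch therefore changes how an SAE is labelled, and any table that uses the label. It changes nothing else in the plan.

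**The case against.** The strongest reply is that the label drives nothing. A necrosis needing surgery or a cast-related limb loss would be recorded, sent to the review board and included in the safety outcome, whatever its label. This stands, and it limits the point to classification and tabulation.

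A reader might infer more, in four ways that the documents do not support.

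- *The safety comparison would flatter the new cast.* The planned test does not use relatedness, the definition applies equally to both arms, and the Background attributes skin problems to the fibreglass cast. If a related-SAE comparison were made, leaving out skin events could favour either arm.
- *The error has a size in percentage points.* With 30 patients and an assumed 1:1 allocation (the ratio is not stated), one patient is 1/15 = 6.7% of an arm. That is only the weight of one patient. The plan specifies no related-SAE rate to which it would apply.
- *The excluded events are those a cast is most likely to cause.* The documents give no frequencies for any of the three categories.
- *The lower stiffness and load to failure of the new cast make the gap more serious.* The Background says that this difference was judged not clinically significant, and nothing links it to skin necrosis or limb loss.

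It can also be said that a causality judgement is a new procedure and not mere rewording. That is fair, and it is counted as a cost of the fix. None of these replies makes the two definitions consistent.

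**Conclusion.** The point holds as an incorrect classification rule, not as a missing detail and not as a biased comparison. Two of the three SAE categories fall outside the study-related definition unless compartment syndrome is also present, and every compartment syndrome falls inside it whatever its cause. The conclusion rests on reading the second definition as closed, which is how it is worded, and on treating the cast as the study intervention in both arms, which the Study design and randomization section supports. It needs no assumption about event rates or allocation. The consequence is limited to any study-related SAE figure that is reported. That figure could be too low by omission or too high by automatic inclusion, and the documents do not show which arm would gain. It is worth correcting because the figure would describe a new device in a trial without a data safety monitoring board, and the correction costs very little.

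**What to change.** Reconcile the two lists in the Adverse events reporting section. Define a study-related SAE as any event on the SAE list that is judged related to the study cast or its application. This removes both faults: the excluded categories can then count as study-related, and a compartment syndrome with another cause need not. State in the Data analysis section that SAEs will be reported by arm, both overall and by relatedness.

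The cost is a change of wording, a short causality judgement for each SAE with a place to record it, and a related-SAE count that may be higher than under the present definition. Treatment, visits, sample size and the planned tests are unchanged.
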